## **8.2 Responsibility for Analyses/In-House Blinding**

The statistical analysis of the data obtained from this study will be the responsibility of the Clinical Biostatistics department of MSD.

This study will be conducted as a double-blind study under in-house blinding procedures. The official, final database will not be unblinded until medical/scientific review has been performed, protocol deviations have been identified, and data have been declared final and complete.

The Clinical Biostatistics department will generate the randomized allocation schedule(s) for study treatment assignment. Randomization will be implemented in an interactive voice response system (IVRS).

Planned interim analyses are described in Section 8.7. Study enrollment is expected to be completed at the time of any interim analyses. Blinding to treatment assignment will be maintained at all investigational sites. The results of interim analyses will not be shared with the investigators prior to the completion of the study. Subject-level unblinding will be restricted to an external unblinded statistician and scientific programmer performing the interim analysis for the DMC, who will have no other responsibilities associated with the study.

The external Data Monitoring Committee (DMC) will serve as the primary reviewer of the unblinded results of the interim analyses and will make recommendations for discontinuation of the study or modification to an Executive Oversight Committee (EOC). Depending on the recommendation of the DMC, a regulatory submission may be prepared. If the DMC recommends modifications to the design of the protocol or discontinuation of the study, this EOC and limited additional personnel may be unblinded to results at the treatment level in order to act on these recommendations. The extent to which individuals are unblinded with respect to results of interim analyses will be documented. Additional logistical details, revisions to the above plan, and data monitoring guidance will be provided in the DMC Charter.

Prior to final study unblinding, the external unblinded statistician will not be involved in any discussions regarding modifications to the protocol, statistical methods, identification of protocol deviations, or data validation efforts after the interim analyses.

## **8.3 Hypotheses/Estimation**

Objectives and hypotheses of the study are stated in Section 3.0. The study is considered to have met its primary objective in the study population if the combination of pembrolizumab and epacadostat is superior to the pembrolizumab and placebo in PFS at an interim PFS analysis or at the final analysis (i.e., interim analysis 2) or in OS at an interim OS analysis or at the final OS analysis.

## **8.4 Analysis Endpoints**

Efficacy and safety endpoints that will be evaluated for between-treatment differences are listed below, followed by the descriptions of the derivations of selected endpoints.

### **8.4.1 Efficacy Endpoints**

#### **Dual-Primary**

##### **Progression-Free Survival – RECIST 1.1**

Progression-free survival (PFS) is defined as the time from randomization to the first documented disease progression per RECIST 1.1 based on independent central review or death due to any cause, whichever occurs first. See Section 8.6.1.1 for definition of censoring.

##### **Overall Survival**

Overall Survival (OS) is defined as the time from randomization to death due to any cause. Patients without documented death at the time of the final analysis will be censored at the date of the last follow-up.

#### **Secondary**

Duration of response (DOR) determined by disease assessment is defined as the time from the earliest date of qualifying response until earliest date of disease progression or death from any cause, whichever comes first based upon blinded independent radiologists' RECIST 1.1 assessment.

Objective response rate (ORR) is defined as the proportion of the subjects in the analysis population who have a confirmed complete response (CR) or partial response (PR) based on RECIST 1.1 by independent central review.

### **8.4.2 Safety Endpoints**

Safety measurements are described in Section 8.6.2.

## **8.5 Analysis Population**

### **8.5.1 Efficacy Analysis Population**

The Intent to Treat (ITT) population will serve as the population for the analysis of efficacy data in this study. The ITT population consists of all randomized subjects.

Subjects will be included in the treatment group to which they are randomized for the analysis of efficacy data. Details on the approach to handling missing data are provided in Section 8.6 Statistical Methods.

### **8.5.2 Safety Analysis Populations**

The All Subjects as Treated (ASaT) population will be used for the analysis of safety data in this study. The ASaT population consists of all randomized subjects who received at least one dose of study treatment. Subjects will be included in the treatment group corresponding to the study treatment they actually received for the analysis of safety data using the ASaT population. For most subjects this will be the treatment group to which they are randomized. Subjects who take incorrect study treatment for the entire treatment period will be included in the treatment group corresponding to the study treatment actually received

At least one laboratory or vital sign measurement obtained subsequent to at least one dose of study treatment is required for inclusion in the analysis of each specific parameter. To assess change from baseline, a baseline measurement is also required.

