## 2.0 TRIAL DESIGN

### 2.1 Trial Design

**NOTE: As of Amendment 10, the epacadostat/placebo combination therapy is removed from both treatment groups. All subjects remaining in the trial continue on pembrolizumab alone in an open-label fashion. The Second Course retreatment phase is removed. The last trial visit is the Safety Follow-up Visit.**

This is a randomized, placebo-controlled, parallel-group, multi-site, double-blind trial of pembrolizumab and epacadostat in subjects with unresectable or metastatic melanoma to be conducted in conformance with Good Clinical Practices. This Phase 3 study will be conducted in subjects with unresectable or metastatic melanoma. Subjects will be stratified by programmed cell death ligand 1 (PD-L1) expression (positive versus negative/indeterminate) and BRAF mutation status (BRAF mutant and received prior BRAF directed treatment, BRAF mutant with no prior BRAF directed treatment and BRAF wild type) and then be randomized 1:1 (active:placebo) to Treatment A (pembrolizumab + epacadostat) or Treatment B (pembrolizumab + placebo). No treatment crossover is planned.

The treatment period with the combination therapy will continue every 21 days for up to 35 cycles (approximately 2 years) as long as subjects are receiving benefit from treatment and have not had disease progression or met any criteria for study withdrawal.

Specific procedures to be performed during the trial, as well as their prescribed times and associated visit windows, are outlined in the Trial Flow Chart - Section 6.0. Details of each procedure are provided in Section 7.0 – Trial Procedures.

This trial will use an adaptive design based on pre-specified criteria, using an independent, external Data Monitoring Committee (DMC) to monitor safety and efficacy. There will be 2 interim analyses, as stated in Section 8.7.

Results of the interim analysis will be reviewed by the external DMC, which will make recommendations to continue, modify or end the trial according to the plan described in detail in Section 8.0 - Statistical Analysis Plan.

An interim review of the data indicated no benefit of epacadostat over placebo when combined with pembrolizumab. The external DMC recommended that all subjects be unblinded and all epacadostat and placebo administration stop. The study will remain open so that subjects still on study will have continued access to pembrolizumab.

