From the time of treatment allocation/randomization through 30 days following cessation of treatment or if the subject initiates new anticancer therapy, whichever is earlier, all adverse events must be reported by the investigator. Such events will be recorded at each examination on the Adverse Event case report forms/worksheets. The reporting timeframe for adverse events meeting any serious criteria is described in section 7.2.3.1. The investigator will make every attempt to follow all subjects with nonserious adverse events for outcome.

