## **7.2.3 Immediate Reporting of Adverse Events**

### **7.2.3.1 Serious Adverse Events**

A serious adverse event is any adverse event occurring at any dose or during any use of MSD's product that:

- Results in death;
- Is life threatening;
- Results in persistent or significant disability/incapacity;
- Results in or prolongs an existing inpatient hospitalization;
- Is a congenital anomaly/birth defect;
- Is an other important medical event.

**Note:** In addition to the above criteria, adverse events meeting either of the below criteria, although not serious per ICH definition, are reportable to MSD in the same timeframe as SAEs to meet certain local requirements. Therefore, these events are considered serious by MSD for collection purposes.

- Is a new cancer (that is not a condition of the study);

- Is associated with an overdose.

Refer to [Table 10](#) for additional details regarding each of the above criteria.

For the time period beginning when the consent form is signed until treatment allocation/randomization, any serious adverse event, or follow up to a serious adverse event, including death due to any cause, other than progression of the cancer under study (reference Section 7.2.3.3 for additional details) that occurs to any subject must be reported within 24 hours to MSD if it causes the subject to be excluded from the trial, or is the result of a protocol-specified intervention, including but not limited to washout or discontinuation of usual therapy, diet, placebo treatment or a procedure.

For the time period beginning at treatment allocation/randomization through 90 days following cessation of treatment, or 30 days following cessation of trial treatment if the subject initiates new anticancer therapy, whichever is earlier, any serious adverse event, or follow up to a serious adverse event, including death due to any cause other than progression of the cancer under study (reference Section 7.2.3.3 for additional details) whether or not related to MSD's product, must be reported within 24 hours to MSD either by electronic media or paper. Electronic reporting procedures can be found in the EDC data entry guidelines. Paper reporting procedures can be found in the Investigator Trial File Binder (or equivalent).

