
Sample Size and Power
	
The planned sample size was initially approximately 600 subjects. Japan will begin enrolling late in the enrollment period, and must meet a minimum enrollment regulatory requirement. Therefore enrollment from Japan may continue after enrollment in other countries ends. Total enrollment is now expected to be approximately 700 subjects. For PFS, the trial has ~98% power to demonstrate that pembrolizumab and epacadostat is superior to pembrolizumab and placebo at an overall 1-sided 1.25% alpha-level. For OS, the trial has ~79% power to demonstrate that pembrolizumab and epacadostat is superior to pembrolizumab and placebo at an initial overall 1-sided 1.25% alpha-level. Should the PFS comparison be statistically significant, the 1.25% alpha will be re-assigned to OS. Should the OS comparison be statistically significant, the 2.5% alpha will be re-assigned to ORR. Should the total alpha assigned to OS be 2.5%, the power to demonstrate improved OS with the combination will be about 86%. The treatment effect (true hazard rate) is assumed to be 0.65 for PFS and 0.70 for OS.

Based on review of IA2 data, the DMC recommended that all subjects stop oral therapy (epacadostat/placebo). After study completion, only selected analyses will be performed.

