The threshold of at least 4 events was chosen because the 95% confidence interval for the between-group difference in percent incidence will always include zero when treatment groups of equal size each have less than 4 events and thus would add little to the interpretation of potentially meaningful differences. Because many 95% confidence intervals may be provided without adjustment for multiplicity, the confidence intervals should be regarded as a helpful descriptive measure to be used in review, not a formal method for assessing the statistical significance of the between-group differences in adverse events and predefined limits of change.

Continuous measures such as changes from baseline in laboratory, vital signs, and ECG parameters will be considered Tier 3 safety parameters. Summary statistics for baseline, on-treatment, and change from baseline values will be provided by treatment group in table format. In addition, summary statistics for the difference between treatment groups will also be provided, along with nominal p-values for between-group differences. Mean change from baseline over time will be plotted with the corresponding standard errors.

The broad clinical and laboratory AE categories consisting of the percentage of subjects with any AE, a drug related AE, a serious AE, an AE which is both drug-related and serious, and who discontinued due to an AE will be considered Tier 2 endpoints. Ninety-five percent confidence intervals (Tier 2) will be provided for between-treatment differences in the

percentage of subjects with events; these analyses will be performed using the unstratified Miettinen and Nurminen method [57], an unconditional, asymptotic method.

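### The safety plan sets no cut-off at the epacadostat/placebo stop, so by default adverse events on open-label pembrolizumab alone still count to the original arms

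*Combined protocol and SAP*

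**What the plan says.** - **Grouping (8.5.2).** "Subjects will be included in the treatment group corresponding to the study treatment they actually received". The only departure from the randomized group that is described concerns "Subjects who take incorrect study treatment for the entire treatment period". A subject who gave up epacadostat or placebo part-way therefore stays in the original arm.
- **Treatment after the stop (2.1).** "The external DMC recommended that all subjects be unblinded and all epacadostat and placebo administration stop". After that, "All subjects remaining in the trial continue on pembrolizumab alone in an open-label fashion". Table 1 allows up to 35 infusions.
- **Event collection (7.2 and 7.2.3.1).** Adverse events are reported "From the time of treatment allocation/randomization through 30 days following cessation of treatment", or until new anticancer therapy if earlier. Serious events are reported "through 90 days following cessation of treatment, or 30 days following cessation of trial treatment if the subject initiates new anticancer therapy".
- **Comparison (8.6.2, Table 13).** Tier 2 gives 95% confidence intervals for the between-arm difference in the percentage of subjects with an event, and "these analyses will be performed using the unstratified Miettinen and Nurminen method".
- **Exposure (8.12).** Exposure is summarized as duration of treatment in cycles, with no split at the stop.
- **Amendment 10 note (8.1).** After completion only a limited, unlisted set of analyses will be done. The Summary of Changes adds that the analysis may be modified and reported in the clinical study report.

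No section gives an at-risk window for epacadostat, a data cut for the comparative safety tables, or a separate period for pembrolizumab alone.

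**The concern.** Section 3.2 makes safety and tolerability of the two treatment groups a secondary objective. The contrast that serves it is pembrolizumab with epacadostat against pembrolizumab with placebo. Once the oral drug stops, the arms no longer differ in treatment, and everyone can know the earlier assignment. First events from that period say nothing about adding epacadostat, and reporting and causality judgments are no longer blind.

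Data capture also changes. According to the Summary of Changes, laboratory tests from Cycle 4 become standard of care, and the text on attributing an event to the combination or to one agent is removed. Both feed Tier 2 rows: laboratory events, predefined limits of change, and drug-related events. Mixing the two periods can pull the contrast towards the null and adds differences in ascertainment that blinding no longer controls.

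**Working it through.** **1. The plan's own figure.** The only number behind the safety comparison is the Tier 2 threshold of 4 subjects: with fewer than 4 events in each of two equal arms, the 95% interval always includes zero (8.6.2). About 700 subjects randomized 1:1 give 350 per arm. The Miettinen-Nurminen interval is then -0.23 to 2.49 points for 3 against 0 events (includes zero) and 0.05 to 2.90 points for 4 against 0 (excludes zero). The threshold is reproduced; 300 and 331 per arm give the same answer.

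**2. Who contributes post-stop follow-up.**

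Inputs:
- control PFS with 30% cured and the other 70% exponential with median 4.75 months (8.9.1);
- enrollment over about 12 months (8.9.1), taken as uniform;
- IA2 at about month 24 (8.7.1), whose review led to the stop;
- a cap of 35 infusions every 3 weeks: 35 x 21 = 735 days, or 24.1 months (Table 1).

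Assumption: time on treatment equals PFS up to the cap. The control model is used for both arms because the interim review showed no benefit of epacadostat.

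Let λ = ln 2 / 4.75 = 0.1459 per month, so 12λ = 1.751.
- Stop at month 24 (follow-up 12-24 months): 0.30 + 0.70 x (e^(-12λ) - e^(-24λ)) / 12λ = 0.30 + 0.70 x (0.1736 - 0.0301)/1.751 = 0.357.
- Stop at month 21 (follow-up 9-21 months): 0.30 + 0.70 x (0.2689 - 0.0467)/1.751 = 0.389.
- Stop at month 27: the cap removes subjects with more than 24.1 months of follow-up, so 0.30 x 9.15/12 + 0.70 x (0.1120 - 0.0295)/1.751 = 0.262.

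So about 36% (26-39%) would still be on treatment at the stop. Simulation of the same model gives them a mean of 5.9 further months for a stop at month 24, about 18% of all treatment time (27% at month 21, 10% at month 27).

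**3. Effect on the risk difference.** The documents give no event rates for this trial, so the rates are assumptions. Let f be the share with post-stop follow-up and q the chance of a first event then, given no earlier event. Assume both are equal in the two arms and that staying on treatment is unrelated to earlier events. With g = f x q, the observed incidence is p' = 1 - (1 - p)(1 - g), so RD' = (1 - g) x RD.

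Example: 15% against 10% up to the stop (RD 5.0 points, RR 1.50), f = 0.35:

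| q | g | Arms (%) | RD (points) | RR |
|---|---|---|---|---|
| 5% | 0.0175 | 16.49 vs 11.57 | 4.91 | 1.424 |
| 10% | 0.035 | 17.98 vs 13.15 | 4.83 | 1.367 |
| 20% | 0.07 | 20.95 vs 16.30 | 4.65 | 1.285 |

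Over f = 0.25-0.50 and q = 5-20%, g runs from 0.0125 to 0.10, so the risk difference shrinks by about 1-10%. With 10% against 5%, the ratio falls from 2.00 to between 1.80 and 1.31.

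The conditional definition of q matters. If the same percentage of new subjects were simply added to each arm, the difference would not change. The shrinkage arises because a subject already counted cannot be counted again.

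**4. Unequal reporting after unblinding.** Same example, f = 0.35:
- q of 15% (epacadostat arm) and 10% (placebo arm): 19.46 - 13.15 = 6.31 points.
- q of 10% and 15%: 17.975 - 14.725 = 3.25 points.

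The error can go either way.

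**5. Scale against precision.** With 53/350 against 35/350 the 95% interval is 0.23 to 10.14 points, a half-width of about 5. The dilution in step 3 is 0.09 to 0.35 points.

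**The case against.** The strongest reply is that the plan never says these events will be compared by arm. Sections 7.2 and 7.2.3.1 tell investigators what to report, and 8.5.2 assigns subjects, not events. Section 8.1 limits what will be analyzed after completion, and the Summary of Changes explains that original-design text was kept where deleting it might confuse. A safety table cut at IA2 would contain no post-stop event. The intervals are described as descriptive, there are no Tier 1 events, and epacadostat had already been withdrawn for lack of benefit.

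Much of this stands. A reader might infer that the sponsor has decided to keep counting post-stop events. The documents do not support that: inclusion is only what the unadapted rules yield. Nor does the Amendment 10 edit to 8.6.2 show such a decision, since it only removed a phrase about Tier 1 endpoints from the sentence on continuous measures. A reader might also infer that the comparison no longer estimates the effect of epacadostat, or that unblinding biases it in a known direction. Step 5 shows a small shift on the planned measure, and nothing in the documents fixes the direction of reporting bias.

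What does not stand is that the plan already handles the matter. It commits to no IA2 cut. The split into a later study report in 8.7 applies only if an interim success criterion is met; according to the Summary of Changes, PFS missed its criterion and OS was unlikely to succeed. Leaving the window to be chosen after unblinding is discretion that one sentence would remove.

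**Conclusion.** The gap is real and modest. Followed as written, 7.2, 7.2.3.1, 8.5.2 and 8.6.2 place events from a period of identical, unblinded treatment in the original arms. The planned risk difference would shrink by about 1-10% and ratios would move more; differential reporting could add error of either sign.

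The size rests on PFS as a proxy for time on treatment, uniform enrollment, a stop between months 21 and 27, illustrative event rates, and equal conditional post-stop risk in the arms. Discontinuation for reasons other than progression would lower the share with post-stop follow-up. The change is worth making because the rule is cheap and better set in advance; no large distortion has been shown.

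**What to change.** In 8.5.2 and 8.6.2, base all between-arm safety tables on events with onset up to the study-wide epacadostat/placebo stop (each subject's stop under the DMC recommendation) plus the plan's own window of 30 days for adverse events and 90 days for serious events, or up to the plan's existing end of collection if earlier. Tabulate later events separately and descriptively as open-label pembrolizumab only, and split exposure in 8.12 the same way.

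The anchor should be the study-wide stop, not each subject's own last oral dose. Section 5.2.1.4 originally let some subjects stop the oral drug permanently and resume pembrolizumab. Anchoring on their last dose would discard later events from the blinded period, possibly unequally by arm. Those events should stay in the comparison.

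The cost is slightly fewer events in the comparative tables and one extra set of tables. No new data are needed, and subject management does not change.

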## **8.6 Statistical Methods**

Statistical testing and inference for efficacy analyses are described in 8.6.1. Efficacy results that will be deemed to be statistically significant after consideration of the Type I error control strategy are described in Section 8.8, Multiplicity. Nominal p-values may be computed for other efficacy analyses, but should be interpreted with caution due to potential issues of multiplicity, sample size, etc. Unless otherwise stated, all statistical tests will be conducted at  $\alpha=0.05$  (2-sided) level.

